In attempting to address the treatment needs of populations with co-occurring substance dependence and other psychiatric disorders, one approach has been to integrate disorder-specific behavioral treatments based on similar disorder features and overlapping treatment elements, treating co-occurring disorders as if they were a "single disorder" (Weiss et al., 2011). Such integrated behavioral treatments have demonstrated evidence of superior outcomes for both disorders (e.g., Lydecker et al., 2010; Mueser et al., 2013; Weiss et al., 2009). Using this model to integrate transdiagnostic treatment for anxiety disorders with behavioral therapy for opioid dependence has potential to increase the efficiency of treatment and to improve outcomes for both disorders. Specifically, anxiety disorders and opioid dependence: (1) share a number of overlapping features, such as elevated distress intolerance (McHugh et al., 2011); (2) are treated using similar core elements (e.g., functional analysis, skills for coping with emotion- or craving-driven urges); and, (3) are characterized by symptoms that interact (e.g., the use of opioids to manage anxiety; Rigg et al., 2010). The integration of behavioral treatments for anxiety disorders and opioid dependence could capitalize on these overlapping and interacting features. For example, stress reactivity (the emotional and physiological response to a stressor) is implicated as a risk factor for the development of anxiety disorders (McLaughlin et al., 2010) and substance dependence (Koob, 2009), and elevated stress reactivity is associated with worse treatment outcome for both disorder types (e.g., Abelson et al., 1996; Sinha et al., 2006). Thus, understanding this shared vulnerability may be critical to the treatment of co-occurring opioid dependence and anxiety disorders. Studies indicate that elevated stress reactivity predicts poorer treatment response in substance-dependent patients (Sinha et al., 2006, 2011); however, this has yet to be examined in those with co-occurring anxiety disorders. Given the potential link between stress reactivity and outcome for both disorders independently, examination of whether a treatment for their co-occurrence reduces stress reactivity may provide insight into a mechanism of treatment change.

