Perceived Stress Scale (PSS). The Perceived Stress Scale (Cohen, Kamarck, & Mermelstein, 1983) is a 4-item measure that evaluates the extent to which individuals perceive the events in their life as stressful. The PSS has demonstrated adequate test-retest reliability, external validity, and predictive validity (for severity of symptoms, health service utilization, and smoking cessation outcome). The PSS will be administered at both baseline and post-treatment assessments and will be used to evaluate individual differences in perceived stress in order to appropriately analyze stress reactivity data.

Perseverative Thinking Questionnaire. The Perseverative Thinking Questionnaire (PTQ; Ehring et al., 2011) is a 15-item self-report measure of repetitive negative thinking. It has demonstrated excellent internal consistency reliability and satisfactory re-test reliability, in addition to strong convergent and predictive validity. As the PTQ was developed to measure repetitive negative thinking as a transdiagnostic process, it has been studied in various clinical populations (Ehring et al., 2011).

Positive and Negative Affectivity Scale (PANAS). The PANAS (Watson, Clark, & Tellegen, 1988) was developed as a brief measure of affect and yields the factors of Positive Affectivity (PA) and Negative Affectivity (NA). Internal consistency for both scales is high. The PA subscale will be administered at baseline, mid-, and post-treatment.

Primary Anxiety Symptom Measure. Participants will also be asked to complete a measure of anxiety symptoms for the primary anxiety disorder diagnosis identified at baseline. This will include the following measures: Penn State Worry Questionnaire (Meyer et al., 1990) for generalized anxiety disorder, Social Interaction Anxiety Scale (Mattick & Clarke, 1998) for

social anxiety disorder, Panic Disorder Severity Scale-Self Report (Houck et al., 2002) for panic disorder, Body Sensations Questionnaire (Chambless, Caputo, Bright, & Gallagher, 1984) for agoraphobia, and Fear Questionnaire (Marks & Matthews, 1979) for specific phobias.

Quick Inventory of Depressive Symptoms (QIDS). The QIDS (Rush et al., 2003) is a 16-item self-report measure of depressive symptoms. The QIDS has been validated for measurement in clinical trials to assess change and will be used as a measure of depressive symptoms during the trial.

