The stress reactivity paradigm includes two imagery conditions (neutral-relaxing, stress related) and a laboratory session. This paradigm will be completed at pre- and post-treatment assessments. During a visit prior to laboratory sessions, participants will complete two Scene Development Questionnaires (Sinha & Tuit, 2012) that are designed to collect information about each imagery condition (a non-drug-related stressful event in their life, and a neutral-relaxing event); scripts for the imagery conditions will be developed using the information collected. Each script will be written, recorded, and edited by trained research staff in order to ensure that scripts are standardized in terms of length and content. During laboratory sessions, participants will listen to each script. The order of the scripts will be randomized. Psychophysiological measures (skin conductance) will be collected before, during, and after each imagery script. Skin conductance response will be collected using a Biopac MP150 system running AcqKnowledge 4.4 software (Biopac Systems Inc., USA) and the Biopac electrodermal activity amplifier (EDA100c). Skin conductance response is used as an index of physiological arousal, and therefore stress reactivity. Subjective measures that will be administered prior to and following each imagery condition include the Positive and Negative Affect Scale (Watson, Clark, & Tellegen, 1988), and the Opioid Craving Scale (Weiss et al., 2003) that has been adapted to assess craving in the present moment (i.e., “right now”). Following each imagery script participants will also be asked to rate how “clearly and vividly” they were able to imagine the scenario on a 10-point visual analog scale.

V.4.4. Urine Toxicology

Participants will provide weekly urine samples to screen for drug use. Although opioid use is the primary outcome for this trial, the presence of other substances of abuse will be used as secondary outcome. We will use the Alere Toxicology iCup 13 panel drug test screening cup, which tests for the presence of the following substances: cocaine, marijuana, opiates, amphetamines, methamphetamines, phencyclidines, benzodiazepines, barbiturates, methadone, tricyclic antidepressants, oxycodone, propoxyphene, and buprenorphine. We will also use a Drug Screen Test Dip Card to test for fentanyl in the urine sample.

V.4.5. Measurement of Sex Hormones and Menstrual Cycle Phase

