The hypothesis that I-CBT will yield greater reduction in opioid use and anxiety symptoms will be tested using separate linear mixed effects models for opioid use (weeks of use in the previous 4 weeks) and anxiety (HARS score) examining the main effect of treatment condition and its interaction with time on each outcome. The correlation among the repeated measures of the dependent variable will be appropriately accounted for via the inclusion of random subject effects (e.g., random intercepts and slopes for time). Covariates will include pre-treatment values of the dependent variable and any baseline demographic or clinical variables identified as necessary covariates in preliminary analyses.

To test the hypothesis that baseline stress reactivity is associated with treatment outcome at post-treatment (week 12), linear regressions will be utilized with primary opioid and anxiety outcomes at week 12 as the dependent variables and post-stress task anxiety, craving, and heart rate variability as independent variables, co-varying for baseline severity and any other covariates identified in preliminary analyses. In addition, to test the hypothesis that reduction in stress reactivity over time will be greater in the I-CBT condition, a linear mixed effects model will be conducted examining whether stress reactivity decreased from pre- to post-treatment and whether groups differed with respect to this change; this analysis will include the main effects of time and group and the time x group interaction. The correlation among repeated measures of the dependent variable will be accounted for via the inclusion of random subject effects.

With repeated assessments over 7 months of study participation, some amount of missing data is inevitable. Extensive efforts will be made throughout all stages of follow-up to minimize missing data by vigorous outreach, including to any participants who elect to dropout of treatment prior to completion. For all of the proposed analyses, we will use statistical methods (e.g., linear

mixed effects models) that incorporate partially observed data on participants who are lost to follow-up.

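### The Aim 3(a) regressions name heart rate variability, whose collection is nowhere described, omit the recorded skin conductance, and use post-stress levels rather than a response

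*Combined protocol and SAP*

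**What the plan says.** The Background (Section I) defines the construct: "stress reactivity (the emotional and physiological response to a stressor"). Specific Aim 3 has two parts: (a) higher reactivity at baseline goes with more opioid use afterwards, and (b) reactivity falls more under ICBT than under IDC.

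Section V.4.3 describes the laboratory task, which has a stress script and a neutral-relaxing script. On timing: "This paradigm will be completed at pre- and post-treatment assessments". On physiology: "Psychophysiological measures (skin conductance) will be collected before, during, and after each imagery script", and "Skin conductance response is used as an index of physiological arousal, and therefore stress reactivity". The only amplifier named is electrodermal. On self-report: "Subjective measures that will be administered prior to and following each imagery condition include the Positive and Negative Affect Scale", together with the Opioid Craving Scale reworded for the present moment.

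Section VI tests Aim 3(a) by linear regression of the week-12 opioid and anxiety outcomes, with "post-stress task anxiety, craving, and heart rate variability as independent variables". It adjusts for baseline severity and for any covariates found in preliminary analyses. Aim 3(b) is a linear mixed model "examining whether stress reactivity decreased from pre- to post-treatment and whether groups differed with respect to this change". It does not say which variable represents stress reactivity.

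**The concern.** Two things do not fit together. First, the analysis names a physiological variable that the procedures do not describe, and leaves out the one they do. An analyst following Section VI has no described data for the heart rate variability term. An analyst who substitutes skin conductance must choose the script, the time window and the scoring, possibly after seeing data.

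Second, the self-report predictors are worded as values after the stress script. A participant who arrives with high craving will tend to score high after the script whether or not the script had any effect. An association driven by resting craving or affect could then be published as stress reactivity predicting outcome. That is the mechanistic claim Aim 3 exists to test.

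**Working it through.** The plan gives no numerical figure for Aim 3, only a qualitative statement about detectable effects, so there is nothing to reproduce. The check is mainly a comparison of sections.

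**1. Trace each Aim 3(a) predictor to its source.**

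| Predictor in Section VI | Source in V.4.1, V.4.3 or Table 1 |
|---|---|
| Post-stress anxiety | No scale labelled anxiety is named at the task; PANAS negative affect is the nearest |
| Post-stress craving | Opioid Craving Scale, before and after each script |
| Heart rate variability | None; Table 1 lists only the paradigm as a whole |
| (not named) | Skin conductance, recorded around each script |

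Of three named predictors, one has no described source, one has no named scale and one is collected. The single physiological signal recorded does not appear in Section VI.

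**2. Level versus response.** The documents give no correlation between pre-script and post-script scores, so this step only illustrates. Let ρ be that correlation, and assume equal standard deviations before and after. Then:

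- correlation of the post-stress level with the resting score = ρ
- correlation of the post-stress level with the pre-to-post change = (1 − ρ)/√(2(1 − ρ)) = √((1 − ρ)/2)

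| ρ (assumed) | Level with resting score | Level with change |
|---|---|---|
| 0.3 | 0.30 | 0.59 |
| 0.5 | 0.50 | 0.50 |
| 0.7 | 0.70 | 0.39 |
| 0.9 | 0.90 | 0.22 |

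Suppose the outcome depends on the resting score alone, with correlation r. The post-stress level then correlates ρr with outcome although the response plays no part. A bare change score correlates −r√((1 − ρ)/2), so it errs in the other direction. At ρ = 0.7 these are 0.70r and −0.39r. With the pre-stress score in the model, both partial correlations are zero. The clinical severity covariate removes part of this only so far as it tracks the resting score.

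Once the pre-stress score is included, change and level give the same reactivity coefficient: b₁(post − pre) + b₂·pre = b₁·post + (b₂ − b₁)·pre. A change score can therefore serve both parts of Aim 3.

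**3. Cost of adjustment.** Section VI gives N = 54 and allows for 20% loss: 54 × 0.8 = 43.2, taken as 43. Residual degrees of freedom = N − p − 1, where p is the number of regressors. One severity covariate is assumed.

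- Separate regression per measure, p = 2 (reactivity, severity): 51 at N = 54, 40 at N = 43. Adding the pre-stress value (p = 3): 50 and 39.
- Joint model, p = 4 (three reactivity measures, severity): 49 and 38. Adding three pre-stress values (p = 7): 46 and 35.

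**4. Opioid outcome.** Specific Aim 3(a) counts days of use. Section VI counts weeks with use over a four-week window, read at week 12. The units differ.

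**The case against.** The strongest reply is that the Section VI phrase lists variables and is not a scoring rule. The sentence is introduced as a test of baseline stress reactivity, V.4.3 collects pre-script and neutral-script values, and the severity covariate might be taken to include a resting score. Some of this stands: the authors may well have intended a response measure. But the text does not say so. Baseline severity most naturally means clinical severity at study entry, and even on the generous reading the reactivity score is undefined.

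Several stronger readings are tempting but not supported:

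- *Heart rate variability was not recorded.* The documents show only that its collection is not described.
- *Skin conductance is the declared measure of reactivity.* V.4.3 calls it an index, and Section I's definition includes an emotional component, so self-report predictors fit the construct.
- *Task anxiety is not measured.* V.4.3 says the subjective measures include PANAS and craving, which leaves room for an unlisted scale. Whether negative affect is available also needs confirming: V.4.3 gives the full PANAS, whereas V.4.1 and Table 1 mention only positive affect at the main assessments.
- *The opioid outcome covers the wrong period.* Section VI restates the hypothesis as outcome at post-treatment, week 12, which is a compatible reading of Aim 3(a). Only the unit clearly differs.
- *Aim 3 is underpowered.* Nothing here contradicts the plan's loose statement of detectable effect. Detectable correlations would price the remedy and not measure the defect.

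**Conclusion.** The point holds and should be fixed before analysis. The physiological test of Aim 3(a) cannot be run as written, because its variable has no described source, while the recorded signal has no stated analysis. This rests on the text alone and needs no assumption. The craving test can be run.

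The level-versus-response problem holds as the regression is worded. Its size cannot be obtained from the documents; the table in the working rests on assumed correlations and equal standard deviations, and shows only the direction and how the error arises.

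For Aim 3(b), skin conductance can be inferred as an outcome, but neither its scoring nor the role of the self-reports is stated. The unnamed anxiety scale and the days-versus-weeks difference are minor. All of this concerns a mechanistic aim of a Stage 1 trial. The Aim 2 treatment comparison is not touched.

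**What to change.** 1. Reconcile Sections V.4.3 and VI on the physiological measure. On the present text, replace heart rate variability in Section VI with skin conductance response to the stress script relative to its pre-script level. If heart rate variability is in fact recorded, describe its collection in V.4.3 and add skin conductance to the analysis.
2. Prespecify one per-person reactivity score for each measure, for example post minus pre for the stress script, or that change minus the corresponding neutral-script change. State the skin conductance window and scoring.
3. Include the pre-stress value as a covariate in each Aim 3(a) regression. Measurement error in that value may leave some residual confounding, which the report should acknowledge.
4. Use the same change or contrast score as the Aim 3(b) outcome, and say which measures count.
5. Minor: name the scale used for task anxiety, and express the opioid outcome in the same unit in Specific Aim 3(a) and Section VI.

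The cost is wording plus about one degree of freedom per measure (51 to 50 in a separate regression at N = 54; 49 to 46 in a joint model). Skin conductance, PANAS, craving and Timeline Follow-Back data are already planned.

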Specific Aim 2. To examine the efficacy of ICBT for the improvement of opioid dependence and anxiety symptoms relative to Individual Drug Counseling (IDC). We hypothesize that patients will report greater pre-post reductions in interviewer-rated anxiety symptoms and less opioid use in ICBT relative to IDC.

Specific Aim 3. To examine the association between stress reactivity and treatment outcome in opioid-dependent patients. We hypothesize that: (a) higher levels of stress reactivity at baseline will be associated with more days of opioid use following treatment, and (b) reductions in stress reactivity from baseline to post-treatment will be greater in the ICBT group relative to the IDC group.

Specific Aim 4. To examine the association between ovarian sex hormones, negative reinforcement bias, and treatment outcome in opioid-dependent patients. We hypothesize that: (a) greater negative reinforcement bias will be associated with poor treatment outcomes, and that this association will be stronger in women than men, and (b) within women, high progesterone will be associated with lower negative reinforcement bias and less severe opioid symptoms (e.g., opioid craving, anxiety severity).

III. SUBJECT SELECTION

Participants will be recruited for a randomized controlled trial of the efficacy, feasibility, and acceptability of ICBT. We aim to enroll 54 participants in this trial, and anticipate that up to 110 participants will need to complete informed consent and screening in order to initiate treatment. Participants will be recruited via either: (1) invitation to participate by a member of the study staff, or (2) self-selection in response to posted advertisements.

III.1. Inclusion/Exclusion Criteria

Subjects will be **included** if they: (1) are age 18 or older, (2) meet *DSM-5* diagnostic criteria for opioid use disorder, (3) are currently receiving pharmacotherapy for opioid dependence (e.g., buprenorphine, buprenorphine-naloxone, naltrexone, Vivitrol), (4) have used opioids illicitly within the previous 90 days, (5) exhibit clinically-significant anxiety defined as a score of 14 or higher on a clinician-rated anxiety symptom severity scale (the Hamilton Anxiety Rating Scale), (6) meet *DSM-5* diagnostic criteria for a current diagnosis of an anxiety disorder, (7) are able to read and provide informed consent, and (8) intend to remain in the geographical area for the duration of the study period.

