Potentially eligible subjects will be asked to complete the Informed Consent process, at which point the subjects will read through the IRB-approved consent form, and will meet with a research staff member who will answer any questions, explain the schedule of study procedures, and review the risks and benefits of the study. Subjects will be informed about the experimental nature, purpose, risks, and benefits of the study in accordance with procedures of the Partners IRB. There will be no time-limit placed on the consenting process. Research staff members understand that the consent is a process and not simply a matter of signing and dating the consent form. Either the PI or one of the Co-Investigators (serving as designees of the PI) will be available to help explain the study and answer questions. Once the subject consents to participate in the study, the subject will sign and date the consent form along with a member of the research staff. The subject will be provided with a copy of the consent form and the original will be stored in a secure location by a member of the study staff.

Participants will be randomly assigned to receive either ICBT or IDC. This randomization will be stratified by the following variables: (1) presence of a medication for anxiety, (2) gender, (3) type of opioid medication (agonist/partial agonist vs. antagonist), and (4) severity (defined by presence vs. absence of opioid use since initiating pharmacotherapy for opioid use).

V. STUDY PROCEDURES

All participants will receive 12 individual weekly sessions of ICBT or IDC and will complete assessments at baseline, week 12, and 1- and 3-month post-treatment follow-up visits. Breath alcohol screens will be conducted at each session and assessment visit to confirm absence of acute alcohol use. Procedures for response to a positive breathalyzer screen are specified below in Section VII. Qualitative exit interviews will be conducted at the completion of treatment. These interviews will focus on issues related to feasibility and acceptability, such as identifying the most and least helpful sessions and areas for improvement. Details of the procedures are included below.

V.1. Eligibility and Baseline Assessment

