Female participants will provide saliva samples and will report descriptive data on menstrual cycle phase in order to measure fluctuations in estradiol and progesterone throughout the study period. Salivary assays of estradiol and progesterone will be performed in duplicate and in

accordance with manufacturer specifications at the Laboratory for Biological Health Psychology at Brandeis University. Saliva samples will be collected using the passive drool method and according to recommended collection procedures. Samples will be collected at baseline (immediately prior to the Escape Go/NoGo Task) and at each weekly session. In addition to measurement of salivary estradiol and progesterone, we will also collect descriptive data on menstrual cycle phase (with the Menstrual Cycle Information form), following recommendations for optimizing measurement of menstrual phase (Allen et al., 2016). Specifically, we will utilize both self-reported onset of menses and weekly hormone data to characterize menstrual cycle phase throughout the trial. We will also assess for presence, type, dose, and compliance with birth control at each time point. Furthermore, using the interviewer-administered Saliva Sample Activity Documentation form, we will collect information on participant activity in the past 12 hours that may affect saliva collection.

VI. BIOSTATISTICAL ANALYSIS

Data from this randomized controlled trial will be analyzed using descriptive and qualitative analytic methods as well as traditional significance tests. Measures of patient satisfaction will be considered along with qualitative exit interviews to determine the acceptability of the treatment. Randomized groups will be compared with respect to baseline demographic and clinical variables using t-tests and chi-square tests; if significant group differences are identified in any variables known to be highly predictive of outcome, these variables will be adjusted for via their inclusion as covariates. These covariates will also be summarized with descriptive statistics and graphical methods to determine the most appropriate way to incorporate them in the analyses (e.g., continuous or categorical representation). All outcome analyses will utilize an intent-to-treat approach, complemented by exploratory completer analyses.

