We do not expect more than a 10% loss to follow-up (see C.4); nonetheless, the sample size of 54 participants was selected to provide adequate degrees of freedom to estimate the treatment effect size and its reliability, even when allowing for up to 20% loss to follow-up. In this Stage 1 trial, we will focus on the estimation of effect sizes and clinically-significant change (as defined by Jacobson & Truax, 1991). If promising results (i.e., presence of clinically-significant change) are detected, these data will provide an estimate of the reliability of the effect to inform power calculations for a larger Stage 2 clinical trial. Although the focus of this trial is the estimate of an effect size and its reliability, we have conducted a power analysis for the proposed sample size; effect sizes are expressed as standardized differences in means for ease of interpretation. For Aim 2, based on unpublished data from previous clinical trials, we anticipate a small correlation between repeated measures of the opioid use outcome ($r < .20$) and a small to medium correlation ($r = 0.42$) for the HARS. Thus, the proposed sample size would provide adequate power (power of at least 0.80) to detect a minimum between-group difference from baseline to end of treatment in the magnitude of a large effect size ($d = .70-.75$). For Aim 3, based on previous studies examining stress reactivity and alcohol and cocaine use following treatment, which have consistently reported medium to large effect sizes (Sinha et al., 2009; 2011), the proposed sample size would provide adequate degrees of freedom to detect an effect size in the range of high medium to large.

VII. RISKS AND DISCOMFORTS

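### The Aim 3(a) week-12 regressions omit treatment arm; the test stays valid, but one added term would recover a little precision at almost no cost

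*Combined protocol and SAP*

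**What the plan says.** Section VI (Biostatistical Analysis) specifies Aim 3(a) as linear regressions. The dependent variables are the primary opioid and anxiety outcomes at week 12. The independent variables are anxiety, craving and heart rate variability after the stress task. The adjustment is described as "co-varying for baseline severity and any other covariates identified in preliminary analyses". No treatment term is listed, and no within-arm or stratified analysis is described, so the natural reading is one regression over both arms.

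The preliminary analyses are defined earlier in the same section. The randomised groups are compared on baseline demographic and clinical variables, and a variable becomes a covariate "if significant group differences are identified in any variables known to be highly predictive of outcome".

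The neighbouring models do name arm. The Aim 2 mixed models examine treatment condition and its interaction with time, and the Aim 3(b) model lists group, time and their interaction.

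Section II (Specific Aim 2) hypothesises "greater pre-post reductions in interviewer-rated anxiety symptoms and less opioid use in ICBT relative to IDC", which concerns the same two outcomes.

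**The concern.** By week 12 participants have had twelve sessions of one of two therapies that the trial hypothesises will differ in effect on the dependent variables. A regression without arm treats whatever difference results as unexplained variation, which widens the interval around the reactivity slope. If the arms happen to differ in baseline reactivity, part of the arm effect also moves into the estimated slope in that particular trial.

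The covariate clause does not close the gap. Arm is the grouping factor in the baseline comparisons, so it cannot emerge from them as a covariate. An analyst following the text would leave arm out. One who added it would be making an unplanned choice, possibly after seeing results.

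**Working it through.** **Inputs from the documents.** Section III: "We aim to enroll 54 participants in this trial". Section IV: "Participants will be randomly assigned to receive either ICBT or IDC". Section VI: up to 20% loss allowed, so 54 × 0.8 ≈ 43 analysed; "power of at least 0.80" for d = .70-.75; repeated-measures correlation below .20 for opioid use and .42 for the HARS.

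**Assumptions.** The allocation ratio is not stated; 1:1 is assumed. Alpha and sidedness are not stated (the text says only "traditional significance tests"); two-sided .05 is assumed. Aim 3 has only a verbal effect size, upper-medium to large, so a range of r = .30 to .50 is used.

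**Step 1: reproduce the plan's figure.** With 27 per arm, no loss and baseline adjustment, the minimum detectable difference is (1.960 + 0.842) × √(2/27) × √(1 − r²). This gives 0.747 at r = .20 and 0.692 at r = .42, matching .70-.75. The figure is therefore the smallest arm difference that 54 participants can detect.

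**Step 2: variance left in the residual.** With 1:1 allocation, arm explains d²/(d² + 4) of outcome variance:
- d = .75: 12.3%
- d = .70: 10.9%
- d = .50: 5.9%
- d = .30: 2.2%

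**Step 3: power with and without arm.** Without arm, the t test has N − 2 degrees of freedom and noncentrality r/√(1 − r²) × √(N − 2). With arm, r is replaced by r/√(1 − R²), where R² is the share from Step 2, and N − 2 by N − 3. Power in percent:

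| N | r | Without arm | With arm, d = .70 | d = .75 | d = .50 | d = .30 |
|---|---|---|---|---|---|---|
| 54 | .30 | 60.5 | 65.1 | 65.9 | 62.5 | 60.7 |
| 54 | .40 | 87.0 | 90.6 | 91.2 | 88.7 | 87.3 |
| 54 | .50 | 98.3 | 99.2 | 99.3 | 98.8 | 98.4 |
| 43 | .30 | 50.3 | 54.3 | 55.1 | 51.9 | 50.2 |
| 43 | .40 | 77.9 | 82.3 | 83.0 | 79.8 | 77.9 |
| 43 | .50 | 95.0 | 97.1 | 97.4 | 96.0 | 95.1 |

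The gain at d = .70-.75 is about 1-5 points at N = 54 and 2-5 at N = 43. At d = .50 it is at most 2 points. At d = .30 it is essentially nil. At d = .20 the lost degree of freedom slightly outweighs the benefit (a loss of 0.1 to 0.6 points).

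**Step 4: check with the planned predictors.** A simulation used three independent reactivity predictors plus baseline severity (r = .42), at d = .70. Power without and with arm was:
- N = 54: 60% and 66% at slope .3; 87% and 91% at .4; 98% and 99% at .5.
- N = 43: 51% and 55%; 77% and 82%; 94% and 97%.

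At d = .75 and N = 43 the gains were slightly larger, for example 75% to 81% at slope .4. Gains can exceed those in Step 3 because slopes here are per within-arm SD and baseline severity has already removed some residual variance. The message is the same.

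**Step 5: bias and chance imbalance.** In the simulation the mean slope was the same with and without arm. With no true association, type I error at d = .70 and N = 54 was 5.2% without arm and 4.7% with it. In a single trial, a reactivity imbalance of δ SD shifts the standardised slope by d(δ/4)/(1 + δ²/4). One standard error of imbalance is 2/√54 = 0.27 SD, giving a shift of about .05 at d = .70-.75; 1.96 standard errors gives about .09. For scale, the standard error of r = .37 at N = 54 is (1 − .37²)/√53 ≈ .12.

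**The case against.** The strongest reply is that nothing is broken. Aim 3(a) asks whether baseline reactivity is associated with later outcome in these patients, and a regression over both arms answers that. This stands.

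Three stronger readings are tempting, and the documents support none of them.

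- **That omission confounds the association.** Reactivity is measured before treatment and arm is randomised, so the two are independent in expectation. The shift in Step 5 is sampling variation that the standard error already reflects. It is largely the same efficiency loss as in Step 3, not a second harm.
- **That the plan expects an arm effect of d = .70-.75.** Section VI gives this as a detectable minimum and says the trial's focus is effect-size estimation. Aim 2 states only a direction. The comparator is an active counselling treatment, so a smaller difference is quite possible, and the benefit then shrinks towards zero.
- **That power is materially inadequate without arm.** This depends on an Aim 3 effect size that the plan does not quantify. At r = .50 and N = 54, power already exceeds 98%.

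What survives is narrower. Arm is missing from this model alone among the neighbouring ones, the covariate rule cannot supply it, and including it costs almost nothing.

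**Conclusion.** The omission is real but its consequence is modest: a less precise, still valid test of a non-primary aim. The gain of about 1-5 power points at N = 54 (2-5 at N = 43) is conditional on an arm effect as large as the detectable limit, and on the assumed two-sided alpha of .05, 1:1 allocation and r = .30-.50. It falls to 2 points or less at d = .50 and is negligible at d = .30 or below. That the regression covers both arms is inferred from its listed terms, since the text does not say so outright. Minor severity; a free improvement.

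**What to change.** State in section VI that each Aim 3(a) week-12 regression includes treatment arm as a fixed covariate, alongside baseline severity and any covariates from the preliminary analyses. The cost is one degree of freedom and a line of text; no new data are needed. It also brings Aim 3(a) into line with the Aim 2 and Aim 3(b) models and removes a choice that could otherwise be made after seeing results.

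Adding baseline reactivity to the Aim 2 mixed model is not an equivalent one-term change. A reactivity main effect there would average over the modelled visits, not estimate the week-12 association. If that form is preferred, it needs reactivity-by-time terms for each reactivity measure. Whether reactivity acts differently in the two arms is a separate question that this change does not address.
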